## **1. GENERAL INFORMATION**

### ***1.1. Identification of trial***

Protocol code: Hyfe-clinical

Title of trial: **Acoustic cough monitoring in the management of patients with known respiratory disease**

### **1.6. Expected duration of trial**

The study will last up to five years.

## **2. BACKGROUND AND JUSTIFICATION OF THE STUDY**

Respiratory diseases are a leading cause of death in both the developed and underdeveloped world, with conditions such as tuberculosis (TB), Chronic Obstructive Pulmonary Disease (COPD), lung cancer and pneumonia collectively causing over 10 million deaths globally every year (Mathers et al. 2009). Furthermore, as of April 2021, the COVID-19 pandemic has affected 133 million people and killed 2.9 million (John Hopkins 2021).

Cough is a cardinal symptom of all these conditions, and it is also related to increased transmission of communicable respiratory diseases, as pathogens typically spread through droplets and aerosols expelled while coughing.

Cough is generally considered to be a conspicuous, easily identifiable symptom, and changes in its frequency and time pattern can provide valuable information to clinicians on aspects such as disease severity (Hall, 2020), progression and even origin. Nonetheless, objective collection of these data is considerably difficult, and greatly depends on subjective, self-reported information provided by patients (Jaeger, Szidon, Doucette, 1995).

Although several alternative electronic recording cough mechanisms exist, these are typically dependent on the use of external systems using microphones to detect noises exceeding pre-defined thresholds, associated with cough's acoustic signature. (Matos et al, 2007, Barton et al. 2012, McGuinness et al. 2012). These systems have several flaws, including their high cost, difficult scalability, continuous recording (which compromises patient's privacy), and incapacity to integrate cough data with other variables such as time and location of individual cough episodes. (Hall et al. 2020).

We propose using a smartphone-based artificial intelligence (AI) system to detect putative cough sounds, which are then relayed to a remote server and analyzed by an AI machine learning model able to classify sounds as coughs or not coughs. The system also records the time and approximate GPS location of the user when a cough was detected. Furthermore, despite having access to the mobile phone's microphone, the app only records putative cough sounds, protecting the user's privacy.

Our team is currently evaluating the efficacy of community-level surveillance using this tool for the early detection of respiratory infection outbreaks in a parallel study conducted in Navarra, Spain.

At an individual level, continuous cough monitoring has also been long-considered a good proxy of response to treatment in patients with chronic pathologies. But the process still depends on either subjective report by patients, or manual counts of cough episodes recorded by specialized instruments. (Decalmer et al, 2007) We now intend to evaluate the efficacy of a mobile acoustic tool to monitor treatment progression and facilitate etiologic diagnosis in patients with chronic cough of unknown origin at the Clínica Universidad de Navarra.

Furthermore, these systems could also be refined to facilitate the identification of patterns associated to specific diseases. Similar strategies have been already used for the screening of asthma (Porter et al, 2019, Sharan et al, 2018), tuberculosis (Prahar et al, 2021) and COVID-19 (Laguarta, Huet, Subirana, 2020), but not in the context of chronic cough, whose clinical diagnosis remains particularly challenging. In this study, we will (i) evaluate the value of AI-enabled cough monitoring systems for screening, diagnosis, and management of respiratory diseases. We will also simultaneously (ii) collect data from patients with a known diagnosis to enrich existing, public disease-annotated cough datasets for the further training of cough-recognition AI systems, and (iii) assess the technical performance of available digital cough monitoring applications.

### **2.1. Investigational diagnostic intervention**

We will evaluate the potential role of the mobile app Hyfe Cough Tracker™ as a tool to screen for, diagnose and support clinical management of respiratory diseases. For example, among other potential applications, we will use digital cough monitoring to monitor response to

treatment in patients with a diagnosis of chronic cough of unknown origin, and compare it with self-perceived improvement, while enriching a dataset of disease-specific annotated coughs. Hyfe Cough Tracker™ has been developed by a multidisciplinary team including medical doctors, data scientists and software developers, for mobiles using Android and IOS operative systems. It runs in the background of the mobile, having constant access to the microphone. However, it only records explosive sound snippets of 0.5 seconds or less. These records are then relayed to a remote server, where they are classified by the convolutional network as “coughs” or “not coughs”. Sounds labeled as coughs are then registered both in the app, and in a dashboard accessible by researchers. Hyfe does not record any sound longer than 0.5 seconds, therefore, it will not register conversations or background sound, protecting the privacy of participants. The algorithm can be used on the recordings from a wearable recording system incorporating a lapel mic, which can be used to monitor cough continuously in the absence of a smartphone (Hyfe Air).

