## **2.2. Diseases under study**

For the current study we will focus on patients who present to the pneumonology, check-ups and infectious diseases outpatient clinic at the Clínica Universidad de Navarra with cough. This includes patients with cough of unknown origin and those with a previously diagnosed respiratory disease. As a symptom, cough: (i) represents an important reason for consultation at the clinic, (ii) represents a diagnostic challenge, and (iii) is an indicator of the efficacy of specific treatments for underlying respiratory conditions.

Examples of these conditions include, but are not limited to:

- **Chronic cough:** Typically considered to be any cough that lasts for 8 weeks or longer. This condition is thought to affect around 10% of the world adult population and can be caused by a myriad of different conditions, including: allergies, sinus infection, asthma, chronic obstructive pulmonary disease (COPD), cancer, gastroesophageal reflux disease (GERD), among others. (Song et al, 2016).

Its diagnostic process is typically lengthy, and largely based on empiric observations of response to different treatment schemes, which is in turn dependent on subjective reports from patients. Designing a method to objectively monitor this process will likely speed up diagnosis and lead to improved clinical outcomes and reduced costs in the healthcare sector.

- **Tuberculosis:** *Mycobacterium tuberculosis* is the leading infectious cause of death in the world, with most cases occurring in low-income countries. Global prevalence is unknown, but 25-47%

of the total population of India, China, the Philippines, and Pakistan (the five countries with the highest burden) are estimated to be infected (Ragonnet, Trauer, Geard, 2019). Chronic cough is a symptom of pulmonary tuberculosis, and a major driver for transmission of the disease (Turner, 2019).

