## **4. DESIGN OF TRIAL**

### **4.1. Global design**

This is a single center study to be carried out at the two campuses of the Clínica Universidad de Navarra, in the cities of Pamplona, and Madrid, Spain.

For the cough-monitoring process, we will use, an Artificial-Intelligence system (AI) that detects and records explosive putative cough sounds and identifies human cough based on acoustic characteristics (see below).

Potential participants either attending the outpatient clinic or hospitalized with a complaint of cough will be invited by their treating physician, or a member of the research team and included in the study by part of the research team. A researcher will instruct participants on how to install and use Hyfe Cough Tracker in their smartphones. If necessary, the researcher might provide participants with a smartphone configured to exclusively run Hyfe Cough Tracker™. Researchers who enroll participants will also be responsible of obtaining informed consent forms personally.

Once turned on, the app will monitor cough. Participants provided with a study phone will be instructed to run the app continuously and keep the study smartphone close to them for the period of monitoring.

Depending on the objective, participants will either be submitted to diagnostic procedures deemed necessary by their attending physician or will receive the treatment recommended by their attending physicians and will be monitored for a variable period.

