### **Generation of annotated cough datasets**

Participants with an etiologic diagnosis at the time of enrollment, or in which it is reached before the end of the monitoring period, will be retrospectively included in disease-annotated datasets, to assess differences in the acoustic patterns of specific diseases with the neural network created by Hyfe.

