## **6. DESCRIPTION OF THE TOOL STUDIED**

[figure not shown]
Hyfe is an AI-enabled mobile app that records short snippets (<0.5 seconds) of putative cough explosive sounds and then classifies them as cough or non-cough using a convolutional neural network (CNN) model. Briefly, the acoustic characteristics of recorded sounds are converted into an image file, which is then processed by an algorithm trained to identify graphical differences in images. This creates an adjustable prediction score, with values above it, resulting in a sound being classified as “cough”, and those below being classified as “non-cough” (Figure 1).

This allows the discrimination of cough-like sounds from the rest. Cough sounds are then matched with time and GPS coordinates.

The preliminary analytical performance of the system, understood as its sensitivity and specificity differentiating cough episodes from similar recorded sounds, has been validated in an ongoing study in the province of Navarra, Spain (Gabaldon-Figueira et al, 2021). Between November 2020 and January 2021, Hyfe™ registered nearly 700,000 putative cough sounds, from 62 recruited participants. Of these, 119,876 were manually classified by human observers, revealing a sensitivity of 96.34%, and a specificity of 96.54% with a cough-positivity score threshold set at 0.85 (Figure 2). However, since these records exclusively include explosive sounds detected by the application’s algorithm (ignoring coughs that might have

been catalogued as non-explosive sounds, and therefore not furtherly analyzed), this analytical performance must be validated in a real-life scenario, comparing it to continuous records obtained from participants.

Hyfe Air is a wearable device with an incorporated wireless lapel microphone. The device's recordings can be run through the same cough-detection algorithm described above, while its results are directly stored in a remote database and are not displayed to participants. While the algorithm is the same, differences in the characteristics of the incorporated microphone compared to those in smartphones suggest that the device's performance might differ from those previously reported, requiring an independent validation process.

*Figure 1: Audio recordings (bottom) are converted to image files (top) and compared with existing datasets using a CNN. Data not published.*

[figure not shown]

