## 9. STATISTICS

### ***9.1. Description of the statistical methods to be used, including the schedule of all the planned intermediate analyses***

For completion of the primary objective

To assess the accuracy of the cough surveillance system to detect cough patterns associated to specific diseases, we will use participants in which an etiologic diagnose is reached before completion of the study. We will search for digital footprints of singular detected cough events, and/or the pattern of cough in time for participants with a given diagnosis.

These records will be used to train a previously developed convolutional neural network to perform respiratory disease cough classification. We will initially use a random split-sample approach (70% derivation & 30% validation) to assess the performance of the newly generated cough classification tool (sensitivity, specificity, positive and negative predictive values, AUC). Performance will then be validated by retrospectively analyzing these participants' coughs with the newly trained AI-network.

The cough classification tool will be supplemented with patient-specific information to assess the incremental value of cough-based multi-variable prediction.

For secondary objective 1

The daily VAS score of participants will be compared to the cough frequency registered by the cough surveillance system. These data will be used to fit a linear regression model to compare self-reported VAS scores to daily cough frequency and calculate a correlation coefficient ( $r$ ). The

average weekly VAS score and cough frequency on week 1, will be compared to that at study withdrawal using a paired t-test, and represented using before-after plots. P values below 0.05 will be considered significant. A similar approach will be used to compare results of the LCQ at the beginning vs the end of the study. Before-after plots will be constructed to represent these differences. This approach is also expected to provide information on the system's capacity to reflect clinical evolution of participants (Primary objective).

For completion of secondary objective 2

Cough registries of participants with an etiologic diagnosis of respiratory disease will be included in annotated datasets. There are no specific statistical analysis required for completion of this objective.

For completion of secondary objectives 3 and 4

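### For diagnoses reached after monitoring starts, the plan neither keeps the tool's cough counts from influencing the diagnostic label nor records whether they did

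*Combined protocol and SAP*

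**What the plan says.** Section 2.1, on Hyfe Cough Tracker, the tool used in the main study: "Sounds labeled as coughs are then registered both in the app, and in a dashboard accessible by researchers". No delay or lock is stated. Section 6 says of the wearable, Hyfe Air, that "its results are directly stored in a remote database and are not displayed to participants". No equivalent sentence covers the Cough Tracker app.

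The reference diagnosis need not exist before monitoring. Section 4.1, under the generation of annotated datasets, includes "Participants with an etiologic diagnosis at the time of enrollment, or in which it is reached before the end of the monitoring period". Section 9.1 sets a later limit for the primary analysis: "we will use participants in which an etiologic diagnose is reached before completion of the study".

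The work-up is left to clinical judgement. Under Section 4.1, "participants will either be submitted to diagnostic procedures deemed necessary by their attending physician", or receive the treatment their physicians recommend. Section 2.2 describes the diagnosis of chronic cough as "largely based on empiric observations of response to different treatment schemes", and adds that this depends on what patients report.

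Section 9.1 uses the resulting diagnoses to train a neural network on single cough events, on cough over time, or on both. Performance is judged by sensitivity, specificity, predictive values and AUC, starting from a random 70/30 split.

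**The concern.** A diagnostic accuracy study needs a reference diagnosis formed independently of the test under evaluation. Here the cough detections exist, and can be known, while some of the reference diagnoses are still being made. If a diagnosis is reached partly because the recorded cough count changed, and a classifier that uses the same count series is then scored against it, part of the agreement is built in. This is partial incorporation bias.

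The 70/30 split does not protect against it, because the derivation and validation parts carry labels formed in the same way. Nor could the problem be repaired afterwards: unless knowledge of the counts is recorded at the time, the affected labels cannot be picked out later. Under Section 7.2 they would also pass into datasets offered for training other systems.

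**Working it through.** The plan states no figure that depends on this point, so there is nothing to reproduce. The check follows the path from tool output to accuracy estimate and asks at each step what the documents establish.

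1. **Are counts available before the diagnosis?** Yes, for some participants. Detections are registered in the app and on the dashboard (Section 2.1). Outpatients are monitored for an initial month and inpatients until discharge (Section 4.1), and diagnoses reached in that window, or later in the study, are eligible (Sections 4.1 and 9.1). A diagnosis already present at enrolment cannot have been shaped by the study's counts.

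2. **Who could know them?**
   - *Researchers:* documented, through the dashboard.
   - *Participants:* the app runs on their own or a study phone. That they see the counts is an inference from Section 2.1 and from the contrast with Hyfe Air in Section 6, but a natural one.
   - *Treating physicians:* dashboard access is not documented. Section 4.1 says that patients "will be invited by their treating physician, or a member of the research team", so these physicians may know of the monitoring. That is not the same as seeing the counts.

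   The clearest route is therefore the participant's own app.

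3. **Could counts affect the diagnosis?** For chronic cough, yes. The diagnosis leans on the patient's account of response to treatment (Section 2.2), and a patient who has seen the count may report accordingly. Section 2.2 itself expects objective monitoring to shorten the diagnostic process, and Section 2 lists help with etiologic diagnosis among the aims.

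4. **Does the classifier use the same information?** In part. Time-pattern features derive from the same detections. The acoustic features in Section 7.2 (frequency, volume, amplitude) are not what the app and dashboard are said to register, so they are less exposed.

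5. **Is there a safeguard?** None was found. The documents contain no masking of the diagnosing physician, no per-disease reference standard, no adjudication and no hold on results until the diagnosis is fixed. The questionnaire in Section 7.1.1 is completed once consent is given, so as scheduled it captures only what is known then.

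6. **Are other objectives affected?** Secondary objectives 3 and 4 use human listeners as the reference and are not.

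7. **Can a size be derived?** No. It would need the share of participants undiagnosed at enrolment, how often knowledge of counts changes a diagnosis, and how often the later classifier agrees with a diagnosis so changed. The documents give none of these.

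**The case against.** The strongest reply is that the tool being judged is not the tool that can be seen. The disease classifier is trained later and applied retrospectively, so its output does not exist when diagnoses are made. This stands. A reader might infer that the index test itself becomes part of the reference standard, but the documents support only that some of its input data may do so. Section 9.1 also leaves open whether time patterns will be used at all.

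The direction of bias can be disputed too. A falling count after a successful treatment may look the same whatever cause is then assigned, and would separate diseases only if the model also carried treatment information. Section 9.1 does not define the patient-specific information it will add. Objective counts might even improve labels that otherwise rest on subjective report. So upward bias is probable but not demonstrated, and any percentage would be invented.

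A reader might also picture a treating physician watching the dashboard. Section 2.1 gives access to researchers, and Section 4.1 distinguishes the treating physician from the research team.

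Finally, a reader might infer a safety problem from Section 6, which says that "this analytical performance must be validated in a real-life scenario". That caveat concerns coughs the detector may miss. Section 6.1 says the study prescribes no treatment, and nothing directs anyone to act on the counts.

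None of this supplies the missing safeguard or record.

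**Conclusion.** The gap is real and limited. For participants diagnosed after monitoring starts, the plan neither prevents knowledge of the counts from reaching the diagnosis nor describes a record of whether it did. Accuracy for time-pattern features may be biased, probably upward, by an amount that cannot be derived.

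The conclusion rests on two assumptions: that participants can see their counts in the app, and that time-pattern features will be used. If either fails, the concern shrinks, though the dashboard route would still need a stated rule.

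It is worth acting on because the guard is cheap and the missing information cannot be rebuilt later. It does not justify basing the headline result only on diagnoses present at enrolment. That would move the estimate away from cough of unknown origin, where the study hopes to help.

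**What to change.** 1. **Record exposure when the diagnosis is made.** For each etiologic diagnosis, whenever reached, record its date and whether the person making it knew of Hyfe counts, either from the dashboard or as shown or reported by the patient from the app. The form completed at consent is not enough for later diagnoses. It is an attachment not seen here and may already ask for a date.

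2. **Report by exposure.** In Section 9.1, give sensitivity, specificity and AUC separately for diagnoses present at enrolment, those made during monitoring (or later in the study) without knowledge of counts, and those made with it. Do not present the last group as independent evidence of accuracy.

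3. **Separate the label from the dashboard.** State that the label used for the classifier is assigned by someone not consulting the dashboard.

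The cost is two data items, one access rule and smaller strata. As an illustration, if the 200 time series per diagnosis in Section 9.2 cover both parts of the split, validation holds 0.30 × 200 = 60, or 60 / 3 = 20 per stratum if evenly spread. Estimates at that level would be imprecise and best treated as descriptive. All participants stay in the study and in the annotated dataset.

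One limit remains. The record will not catch a patient whose account was coloured by the app without the physician knowing, so the middle stratum is cleaner but not fully independent.

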#### **Secondary objectives:**

1. To assess the clinical performance of questionnaire-based clinical cough assessment by comparing cough records generated by Hyfe Cough Tracker™ to self-reported cough scores.
2. To generate databases of cough sounds annotated with demographic and medical data.
3. To determine the sensitivity and specificity of Hyfe Cough Tracker to detect and classify coughs in a controlled environment.
4. To determine the sensitivity and specificity of Hyfe Cough Tracker and Hyfe Air in a real-life setting.

Research questions to be addressed by this project include: (i) Is there a difference in the self-reported cough frequency of participants and that registered with acoustic surveillance systems? And (ii) can acoustic cough patterns facilitate the etiologic diagnosis of patients with chronic cough?

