### **Assessment of correlation with self-reported questionnaires**

Participants will be asked to complete a daily online, standardized 100mm cough visual analogue scale (VAS), as described by Boulet et al in 2015. Participants will also be instructed to fill a validated Spanish version of the Leicester Cough Questionnaire (LCQ) (Muñoz et al, 2016) at the time of recruitment, and again at the end of the monitoring period.

These records will be compared with those registered by the cough surveillance system. We will evaluate the correlation between the mean weekly VAS score and the registered cough frequency.

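### Participants may be able to see their app cough count when they score the daily VAS, and nothing in the plan keeps the self-report separate from the measure it is compared with

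*Combined protocol and SAP*

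**What the plan says.** Section 2.1 names two places where Hyfe Cough Tracker holds its output: "Sounds labeled as coughs are then registered both in the app, and in a dashboard accessible by researchers". Section 6 describes Hyfe Air, which uses the same algorithm, differently: "its results are directly stored in a remote database and are not displayed to participants". No such statement is made about Cough Tracker.

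Section 4.1 makes the participant's own phone the default: "A researcher will instruct participants on how to install and use Hyfe Cough Tracker in their smartphones". Where needed, "the researcher might provide participants with a smartphone configured to exclusively run Hyfe Cough Tracker™". The same section asks participants for a 100 mm cough VAS, completed online every day. The device used for it is not given. Outpatients are monitored for an initial month and inpatients until discharge.

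Section 9.1 sets the analysis for secondary objective 1: "The daily VAS score of participants will be compared to the cough frequency registered by the cough surveillance system". The method is a linear regression with a correlation coefficient. Section 3 puts the research question as: "Is there a difference in the self-reported cough frequency of participants and that registered with acoustic surveillance systems". Section 9.1 adds that the secondary objective 1 analyses should also inform the primary objective, on whether the system reflects clinical evolution.

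**The concern.** Secondary objective 1 assesses questionnaire-based cough reporting by setting it against the app's record. That comparison is informative only if the rating is formed without sight of the record. A participant who has looked at the count may shift the rating towards it, perhaps without intending to. Agreement would then partly reflect the count being copied into the rating.

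The expected effect is a larger r and a smaller apparent gap between self-report and device, so a real difference under research question (i) could be missed. The change in VAS from week 1 to withdrawal could also follow displayed counts, and would then be weaker corroboration of the app for the primary objective. Because viewing is not recorded, the analysis could neither detect nor adjust for this afterwards.

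**Working it through.** **Step 1: is there a route from count to rating?** Setting the sections side by side:

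- Count held in the participant's app: stated in 2.1.
- Count visible to the participant: not stated. It is implied by section 6, which mentions non-display as a feature of Hyfe Air only.
- Daily rating by the same people, compared with that count: stated in 4.1 and 9.1.
- Count masked, VAS entry ordered before viewing, or viewing recorded: found in no section.

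The route is open as the plan is written. Whether participants use it is unknown.

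**Step 2: reproduce the plan's own figure.** Section 9.2 gives 28 participants for secondary objective 1, from effect size 0.35, one predictor, alpha 0.05, power 80% and 10% loss. Taking 0.35 as Cohen's f², the F test with noncentrality f²·N and (1, N − 2) degrees of freedom gives N = 25 (power 0.809). Then 25/0.9 = 27.8, rounded up to 28, so the figure reproduces. The implied correlation is r = √(0.35/1.35) = 0.51.

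**Step 3: illustrate the possible size.** The documents give neither a true correlation nor a degree of influence, so both are assumed here. Let a share w of the standardised rating come from the displayed count and 1 − w from the participant's own perception, which has true correlation r with the count. Take the displayed figure as identical to the analysed frequency. The observed correlation is

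r′ = [(1 − w)r + w] / √[(1 − w)² + w² + 2w(1 − w)r].

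Worked case, r = 0.30 and w = 0.20: the numerator is 0.8 × 0.30 + 0.20 = 0.44. The denominator is √(0.64 + 0.04 + 0.096) = √0.776 = 0.881. So r′ = 0.50.

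| True r | w = 10% | w = 20% | w = 30% |
|---|---|---|---|
| 0 | 0.11 | 0.24 | 0.39 |
| 0.30 | 0.40 | 0.50 | 0.61 |
| 0.51 | 0.59 | 0.66 | 0.74 |

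**Step 4: effect on the test.** With 25 evaluable participants and f² = r′²/(1 − r′²), a true r of 0.30 gives a significant result with probability 33% at w = 0 and 79% at w = 20%. A true r of 0.30 reaches the planned 0.51 at w of about 21%.

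**Step 5: can a split by viewing status test this?** With 25 people divided 12 and 13, the standard error of a difference in Fisher z is √(1/9 + 1/10) = 0.46. The difference between r = 0.50 and r = 0.30 is 0.549 − 0.310 = 0.24 on that scale. The split cannot separate the two.

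**The case against.** The strongest reply is that no section says participants see, open or use a count. Section 2.1 says coughs are registered in the app, which is not the same as displayed, and visibility is inferred from the contrast with Hyfe Air. This stands, and it limits the conclusion to a possible dependence.

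A reader might infer that the VAS is scored on the phone that shows the count. The documents do not support this: section 4.1 says only that the VAS is online, and a study phone dedicated to the app would presumably not be used for it. The point does not need it, because what matters is whether the count has been seen.

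The illustration is also open to challenge. Its inputs are assumed. Section 7.2 analyses a rate per hour of recording, while the app's display is not described. If the display is a raw count and recording hours vary, the inflation for a given w is likely to be smaller. Participants do not see each other's counts, and a VAS has no fixed conversion from coughs to millimetres. Anchoring may therefore act mainly within a person over time, and a simple mixture could overstate its effect on a between-person r. These limits stand, and the table should be read only as a range.

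Finally, the primary objective concerns use in clinical practice, where visible records may be normal. That is a fair reason not to insist on full masking. It does not help secondary objective 1, which needs a rating formed independently of the count.

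**Conclusion.** The point holds as a possible bias. As written, the plan leaves an open route for the app's count to influence the rating it is compared with, and has no means of knowing whether this happened. The likely direction is towards a larger r and a smaller apparent difference. The size cannot be derived from the documents. For assumed influence of 10% to 30%, the rise is 0.11 to 0.39 when the true r is 0, 0.10 to 0.31 when it is 0.30, and 0.08 to 0.23 when it is 0.51.

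Three stronger readings are not supported:

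- That the self-report is definitely not independent. Display is only implied, and use of the count is unknown.
- That the planned r of 0.51 could arise mostly from display. Starting from a true r of 0.30, own perception supplies 0.30 of the 0.51 and display about 0.21.
- That the sample size is wrong. The 28 reproduces and does not depend on this point.

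The week-1 versus withdrawal test on device-measured frequency is not directly contaminated. Only the self-report side of that comparison is exposed.

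**What to change.** In section 4.1, under the questionnaire procedures:

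1. State whether Cough Tracker users can see their counts. If they cannot, one sentence saying so closes the point.
2. If they can, require each day's VAS to be submitted before that day's app cough record is opened.
3. Hide the count on study phones, but only if the app allows it. The documents do not describe such a feature.
4. At the end of monitoring, ask one question on whether counts were viewed.

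In section 9.1, add the correlation by viewing status as a descriptive sensitivity analysis. Viewers are self-selected and the groups are too small for a formal comparison.

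The cost is an instruction, one question and possibly a phone setting. Participants lose some feedback. Own-phone users can only be instructed, and the daily ordering does not fully remove carry-over from counts seen on earlier days. The sample size does not change.
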